1.4 DESIGN FEATURES

Only newly diagnosed cases of sarcoidosis with tissue confirmation of granuloma and a clinical course compatible with sarcoidosis, that is, a systemic granulomatosis of unknown etiology are eligible for the study. Newly diagnosed cases are of interest for accuracy and consistency of recall. A newly diagnosed case is defined as a patient who had tissue confirmation less than six months prior to entry into the study. Initially, cases are recruited at each participating Clinical Center, without regard to type of clinical disease (i.e., erythema nodosum or Löfgren's Syndrome; acute or chronic sarcoidosis, excluding patients with fibrotic lung disease; fibrotic lung disease; or extrapulmonary sarcoidosis). Clinical Coordinating Center staff review the distribution of enrolled cases periodically to ensure that appropriate proportions of cases in each of the defined categories of disease are enrolled.

Population-based controls are selected through random digit dialing. Controls are matched to cases on age (within five years), gender and self-designated race (black, white, other). Random digit dialing facilitates the selection of a control group that approximates a probability sample in the population.

Only individuals 18 years of age or older are eligible. Cases or controls cannot have active tuberculosis or be taking anti-tuberculosis therapy or have a history of chronic beryllium disease. Potential controls with a past history of sarcoidosis, granulomatous hepatitis, primary biliary cirrhosis, Bell's palsy, undiagnosed uveitis, Crohn's disease and erythema nodosum of unknown etiology are excluded from the study. Cases and controls must be competent to sign consent forms for study participation and must be willing to participate in all required study evaluations.

Both cases and controls complete an entry evaluation for the collection of required data and biological specimens for future evaluation. The entry evaluation includes collection of demographic

information (age, gender, race, residence, marital status, etc.), medical history, environmental, and occupational exposure history, questions about the individual's family (first degree relatives), standardized psychosocial data on health related quality of life, and medical care usage.

The first 240 ACCESS cases are asked to participate in a two-year clinical course study. A clinic visit is scheduled between 24 and 30 months after the patient's baseline evaluation. The follow-up evaluation includes a medical history, physical examination, chest X-ray, spirometry, routine biochemistry, complete blood count and differential, and additional tests as clinically indicated. Clinical Center staff also contact these ACCESS cases by telephone at 6, 12 and 18 months after entry.

1.5 STUDY SIZE CONSIDERATIONS

1.5.1 Case Control Study

The proposed sample size of 720 cases and 720 controls for the ACCESS etiology study is adequate to identify associations of exposure variables between cases and controls with odds ratios of two or greater even when the prevalence of the exposure is small (proportion of controls exposed is 0.05). The planned statistical power is important since the etiology of sarcoidosis could be multifactorial and include several low-prevalence exposure agents.

Etiological factors may be different in certain age-race-gender groups. The large number of cases and controls in the ACCESS etiology study will permit stratification of the ACCESS population into smaller groups while maintaining adequate power (at least 80%) to detect moderate effects (odds ratios on the order of 3 or greater) when the prevalence of the exposure in the control group is slightly higher (proportion of controls exposed is 0.10). The large number of cases and controls will also help in determining whether certain groups have different risk factors (tests for interaction).

In certain substudies, large effects have been hypothesized. Even with 180 case and control pairs and a proportion exposed of 0.1 in the control group, the power to detect an odds ratio of 2.0 will be at least 86% (see Chapter 12).

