Tables 1 and 2 show the power of the proposed design to detect specified odds ratios as a function of the correlation (0.5 and 0.0) between case and control exposure rates, and the expected value of the control exposure rate with the alpha level for the test set at 0.05 (two sided test) and with 720 cases. With the proposed number of cases and controls there will be 98.6% power to detect odds ratios of 0.7 or less and 98.8% power to detect odds ratios of 1.4 or greater when the correlation between case and control exposures is 0.5 (Table 1) and the proportion of controls exposed is 0.3. If the correlation between cases and control exposures is 0.0 (a conservative estimate), the power is reduced to 84.3% and 85.1%, respectively. If the proportion of controls exposed is reduced to 0.05 there is at least 90% power to detect an odds ratio of 2.0.

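### Section 1.5.1 states power of at least 86% for 180 pairs, but 86% holds only at an unstated exposure correlation of 0.5; at correlation 0 the protocol's own table gives 60%

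*Protocol*

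**What the plan says.** The protocol's Section 1.5.1 sums up the power of the case control study. For substudies of 180 matched pairs, with 10% of controls exposed, it states: "the power to detect an odds ratio of 2.0 will be at least 86% (see Chapter 12"). It names no correlation between the exposure of a case and that of the matched control.

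Section 12.2.1 gives the matched-pair power formula and says that power is shown "as a function of the correlation (0.5 and 0.0) between case and control exposure rates". Its first two tables are computed "with the alpha level for the test set at 0.05 (two sided test) and with 720 cases". On the lower correlation it says: "If the correlation between cases and control exposures is 0.0 (a conservative estimate), the power is reduced to 84.3% and 85.1%, respectively". It expects matching to produce positive correlation in general, but gives no size.

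Tables 7 and 8 at the end of Chapter 12 both cover 180 pairs. In the row for odds ratio 2.0 and the column for 10% exposure, Table 7 (correlation 0.5) has 0.862 and Table 8 (correlation 0) has 0.601.

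Just before the substudy sentence, Section 1.5.1 also claims that the population can be split by stratum with power kept up: "maintaining adequate power (at least 80%) to detect moderate effects (odds ratios on the order of 3 or greater"). This is for 10% exposure, and no group size is given.

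**The concern.** A power described as at least some value is read as a minimum over the assumptions left open. Here the open assumption is the exposure correlation, and the chapter that the sentence cites contains a value 26 percentage points lower for the same number of pairs, exposure and odds ratio.

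The protocol does not use the wording consistently. For 720 pairs, 5% exposure and an odds ratio of 2.0, Section 12.2.1 also claims a minimum, of 90%. There the minimum is the correlation-0 entry (Table 2, 0.909) and not the correlation-0.5 entry (Table 1, 0.995). A reader who learns the convention from Section 12.2.1 will take 86% as the conservative figure.

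At stake is how a null result for a modest, uncommon exposure in about 180 pairs would be read. A type II error of 14% and one of 40% call for different conclusions.

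**Working it through.** **Inputs.** N = 180 pairs, one control per case, control exposure p0 = 0.10 and odds ratio 2.0 (Section 1.5.1). Alpha is 0.05 two-sided, so z = 1.96; the correlation r is 0.5 or 0 (Section 12.2.1).

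**Formula (Section 12.2.1, one control per case).**
- p1 = OR·p0 / (1 − p0 + OR·p0), and d = p1 − p0
- psi = p1 + p0 − 2·p1·p0 − 2·cov
- power = Φ(d·√(N/psi) − 1.96)

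The tables are labelled by correlation, so I took cov = r·√(p1(1−p1)·p0(1−p0)). With that reading the formula matches 13 checked cells and quoted figures from Tables 1 to 10 to within 0.001.

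**Common terms.** p1 = 0.2/1.1 = 0.1818; d = 0.0818; p1 + p0 − 2·p1·p0 = 0.2455; √(p1(1−p1)·p0(1−p0)) = 0.1157.

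**The protocol's figure, r = 0.5.** psi = 0.2455 − 2 × 0.5 × 0.1157 = 0.1297. Then 0.0818 × √(180/0.1297) = 3.047; 3.047 − 1.96 = 1.087; power = 0.862. This is the Table 7 entry.

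**The conservative case, r = 0.** psi = 0.2455. Then 0.0818 × √(180/0.2455) = 2.216; 2.216 − 1.96 = 0.256; power = 0.601. This is the Table 8 entry.

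**Between the two:**

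| Correlation | 0 | 0.1 | 0.2 | 0.3 | 0.4 | 0.5 |
|---|---|---|---|---|---|---|
| Power | 60.1% | 64.4% | 69.1% | 74.4% | 80.2% | 86.2% |

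Power rises steadily with the correlation, so 86% needs a correlation of practically 0.5.

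**Other test versions at r = 0.** The McNemar unconditional variance gives 60.2%, an unmatched two-proportion test 60.8%, and a one-sided test 71.6%. None reaches 86%.

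**What 180 pairs do detect at r = 0.** At OR 2.36, p1 = 0.2077, d = 0.1077, psi = 0.2662, and power is 80.0%. OR 2.4 gives 81.7% and OR 2.5 gives 85.3%. For OR 2.0 itself, 86% power at r = 0 would need about 339 pairs.

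**The odds ratio 3 claim.** With p0 = 0.10, p1 = 0.25 and d = 0.15; psi = 0.300 at r = 0 and 0.170 at r = 0.5.

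| Pairs | Correlation 0 | Correlation 0.5 |
|---|---|---|
| 50 | 49.1% (Table 12) | 73.0% (Table 11) |
| 100 | 78.2% (Table 10) | 95.3% (Table 9) |
| 180 | 95.7% (Table 8) | 99.8% (Table 7) |

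Power of 80% is reached at 105 pairs for r = 0 (80.1%; 104 pairs give 79.8%) and at 60 pairs for r = 0.5 (80.4%; 59 pairs give 79.8%).

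**The case against.** The best defence is that 86% is a correct entry in the protocol's own Table 7, and that the sentence sends the reader to a chapter where both tables are printed in full. Matching is expected to produce positive correlation, so Table 8 is a lower bound and not the expected power. The worked subgroup example in Section 12.2.3 also uses 0.5, and says so. All of this stands. It disposes of two readings that a reader might infer: that 86% is a miscalculation, and that the true power is 60%. The documents support neither. What the defence does not supply is any reason to treat 0.5 as a minimum, because no expected size is given anywhere.

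A reader might also infer that the substudies rest on this sentence and are therefore underpowered. The documents do not show that. Section 1.5.1 speaks of large hypothesised effects and offers 180 pairs as an illustration. No study in Section 3.6 states 180 pairs, Section 3.6.7 cites its own power calculations for 360 pairs, and Section 3.6.5 mentions its own power analysis.

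Nor does the power for an odds ratio of 2.0 at 100 pairs (37.9% in Table 10, 62.2% in Table 9) describe the cell-wall-deficient-form culture study in Section 3.6.4. That study cites about 80% positive cultures in patients against fewer than 15% in volunteers, an odds ratio of at least about (0.80/0.20)/(0.15/0.85) = 23. Table 10 already gives 1.000 for an odds ratio of 10 at 10% and at 30% exposure. Section 3.6.3, also at 100 pairs, states no effect size to judge against.

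Finally, a reader might conclude that the odds ratio 3 claim fails for small subgroups in general. At 100 pairs it misses 80% narrowly, and only at correlation 0; there 80% is reached at an odds ratio of about 3.07, which fits the protocol's loose wording. Only about 50 pairs fail clearly. Section 12.2.3 links its 7% and 14% sizes (about 50 and 100 of 720 pairs) to small substudies, whereas the odds ratio 3 claim concerns age-race-gender groups whose size is not stated.

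**Conclusion.** The statement is wrong as worded. For 180 pairs, 10% exposure and an odds ratio of 2.0, the protocol's calculations support a range of 60% to 86% over correlations from 0 to 0.5. Section 1.5.1 presents the upper end as a minimum and leaves out the assumption that produces it. On the case that the protocol labels conservative, the shortfall is 26 percentage points (86.2% less 60.1%).

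This rests on the protocol's own formula, a two-sided 5% test, and correlation read as the correlation of exposure within pairs, which reproduces the tables. It does not depend on which correlation will be observed: any value clearly below 0.5 breaks the claim. The odds ratio 3 sentence is a lesser matter, a claim without the subgroup size that it needs. Neither point shows that a planned substudy is too small.

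**What to change.** Restate the substudy sentence along these lines: with 180 pairs and 10% of controls exposed, power for an odds ratio of 2.0 is about 86% if the case-control exposure correlation is 0.5 and about 60% if it is 0 (Tables 7 and 8); at correlation 0, power of 80% is reached at an odds ratio of about 2.4.

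As a minor addition, attach a size to the odds ratio 3 sentence: at 10% exposure, power is at least 80% from about 105 pairs at correlation 0, or about 60 pairs at correlation 0.5, and is 49% to 73% at 50 pairs (Tables 12 and 11).

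The cost is two reworded sentences and a less favourable stated power. Sample size, analysis and conduct do not change.

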3.6.3 Searching for an Infectious Etiology for Sarcoidosis

To investigate the hypothesis that sarcoidosis is the result of a response to an infectious agent, the prevalence of micro-organism DNA is determined using broad based PCR for the

detection of 16s-rDNA for micro-organisms in the domain Bacteria, Eukarya and Archaea, in blood samples from both cases and controls.

This project seeks to identify a putative infectious etiology for sarcoidosis by examining blood samples from 100 cases and their matched controls using PCR technology. The broad based infectious organism search uses 16s ribosomal RNA phylogeny; and will examine the 16s-DNA coding the ribosomal RNA. Any DNA that is recovered using this broad-based strategy will be sequenced to determine the possible origin. Preliminary results using broad based primers as well as primers specifically for Mycobacterium tuberculosis have shown that the methodology is applicable to blood samples with a recovery from 100 to 1 organism equivalent per sample.

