3.6.4 Role of Mycobacterial Cell Wall Deficient Forms in Sarcoidosis

Since Schaumann's description of "peculiar corpuscles" present in the tissue of patients with sarcoidosis (Schaumann, 1941), an increasing body of evidence has implicated various infectious organisms, particularly mycobacteria, as the etiologic agent(s) in sarcoidosis. Judge, Graham, Khomenko, Barth and Almenoff (Judge and Mattman, 1976; Barth et al, 1979; Khomenko et al, 1987; Graham et al, 1988; Almenoff et al, 1996) have grown mycobacterial cell wall deficient forms (CWDF) from blood and tissue of patients with sarcoidosis. Approximately 80% of patients with sarcoidosis have had cultures positive for CWDF, and fewer than 15% of normal volunteers have had cultures positive for CWDF (Almenoff et al, 1996). However, conflicting results have been obtained using molecular biologic techniques to detect mycobacterial DNA in tissue, broncho-alveolar (BAL) fluid and blood of patients with sarcoidosis. In this study cultures for CWDF are made on 100 cases and 100 controls using techniques already established in the investigator's laboratory, and the species of organism(s) isolated are identified using molecular biologic techniques.

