6.3.1 Random Digit Dialing Controls

Cases are matched in a one to one ratio to controls selected through random digit dialing. Random digit dialing facilitates the selection of a control group that approximates a probability sample in the population. Random digit dialing (RDD) is used to identify potential controls through an unbiased clustered random sample of households with telephones (Waksberg, 1978). Cluster sampling of telephone households and a stratified sample of age-, gender-, and self-identified racematched individuals are used (Hartge et al, 1984).

The groups selected to generate telephone numbers, Survey Sampling Inc. (SSI), and to perform the telephone recruitment of potential controls, Telesurveys Research Associates (Random Digit Dialing (RDD) Interview Group), work under the direction of the Clinical Coordinating Center. The RDD callers are responsible for making initial telephone contact with potential controls in the geographic areas of the Clinical Centers.

Once the RDD Interview Group recruiter has established the eligibility, availability and willingness of the potential control to participate, the potential control is informed that an interviewer from the Clinical Center will be in touch soon to set up an appointment to meet for questionnaire

administration and phlebotomy. Potential controls are informed that a payment will be given to them after they complete the study interview to reimburse them for parking costs, meals and other expenses (including lost time from work) at the medical center, and transportation costs.

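### Section 1.5.1 gives 86% as a minimum power for 180 pairs, but it is the favourable of two tabulated values (60.1% at correlation 0), and no stated substudy size is 180 pairs

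*Protocol*

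**What the plan says.** Section 1.5.1 (Case Control Study) notes that some substudies expect large effects. It then claims that "the power to detect an odds ratio of 2.0 will be at least 86" per cent, with a pointer to Chapter 12. The setting for that claim opens the same sentence: "Even with 180 case and control pairs and a proportion exposed of 0.1 in the control group". It gives no correlation between the exposures of a case and its matched control.

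Chapter 12 tabulates power at two correlations, 0.5 and 0. Section 12.2.1 introduces the second with the words "If the correlation between cases and control exposures is 0.0 (a conservative estimate". For an odds ratio of 2.0 and 10% of controls exposed:

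| Pairs | Correlation 0.5 | Correlation 0 |
|---|---|---|
| 180 | 0.862 (Table 7) | 0.601 (Table 8) |
| 100 | 0.622 (Table 9) | 0.379 (Table 10) |

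On size, section 12.2.3 associates a small substudy with 7% and 14% of the study population; 180 pairs is its 25% subgroup. Section 3.6.3 plans on "examining blood samples from 100 cases and their matched controls using PCR technology". Section 3.6.4 says "cultures for CWDF are made on 100 cases and 100 controls". Section 3.6.7 gives 360 cases and matched controls for immunogenetics. Section 3.6.2 (differential display) screens 20 cases and 20 controls, with a further 10 and 10, and section 3.6.6 (T cells) studies 20 cases. Section 3.6.1 (HLA) states no number, and the size in section 3.6.5 (Kveim) cannot be read in the text available.

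**The concern.** A stated minimum tells the reader that power is no lower under any assumption the plan regards as plausible. Here the number is the better of two values that the plan itself prints, and the assumption that produces it is left out.

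The protocol uses the same expression differently elsewhere. In section 12.2.1, the claim of at least 90% power for an odds ratio of 2.0 with 720 cases and 5% of controls exposed is a true floor over the two correlations: Table 2 (correlation 0) gives 0.909 and Table 1 (correlation 0.5) gives 0.995. A reader who carries that usage over to section 1.5.1 will be misled.

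The choice of 180 pairs adds to this. The sentence is there to reassure about substudies, and its opening words suggest that even a small one is well placed at an odds ratio of 2.0. The section 3.6.3 search by polymerase chain reaction (PCR) has 100 pairs, and its description states neither an expected effect nor a power. The 180-pair figure is therefore the overview statement a reader is most likely to apply to it.

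**Working it through.** **Inputs**
- Two-sided test: "the alpha level for the test set at 0.05 (two sided test) and with 720 cases" (section 12.2.1), so z = 1.96. The same alpha heads Tables 7 to 10.
- "a proportion exposed of 0.1 in the control group" (section 1.5.1): p0 = 0.10.
- Odds ratio 2.0 (section 1.5.1).
- "Cases are matched in a one to one ratio to controls selected through random digit dialing" (section 6.3.1): one control per case.
- Correlation ρ = 0.5 or 0 (Chapter 12 tables).

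**Formulas.** With one control per case, the section 12.2.1 formula reduces to

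power = Φ(δ·√(N/ψ) − 1.96), with δ = p1 − p0 and ψ = p1 + p0 − 2·p1·p0 − 2·cov.

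I take p1 = OR·p0 / (1 + p0·(OR − 1)) and cov = ρ·√(p1(1−p1)·p0(1−p0)). The protocol does not spell out these two steps, but they reproduce its tables.

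**Common quantities**
- p1 = 0.20/1.10 = 0.1818, so δ = 0.0818.
- ρ = 0: ψ = 0.2818 − 0.0364 = 0.2455.
- ρ = 0.5: 2·cov = √(0.1818 × 0.8182 × 0.10 × 0.90) = 0.1157, so ψ = 0.2455 − 0.1157 = 0.1297 (from unrounded values).

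**Reproducing the stated figure, 180 pairs**
- ρ = 0.5: 0.0818 × √(180/0.1297) = 3.05; Φ(3.05 − 1.96) = **0.862**, matching Table 7.
- ρ = 0: 0.0818 × √(180/0.2455) = 2.22; Φ(2.22 − 1.96) = **0.601**, matching Table 8.

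Between these, power is 71.7% at ρ = 0.25. Reaching 80% needs ρ of about 0.40, and reaching 86% needs about 0.497. The figure therefore holds as a floor only if the correlation is essentially 0.5 or more. A McNemar calculation with the unconditional variance changes little: 0.868 at ρ = 0.5 and 0.602 at ρ = 0.

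**Size of substudy.** 7% of 720 is 50.4 and 14% is 100.8, that is, about 50 and 100 pairs; 25% is 180.

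**Same odds ratio and exposure, 100 pairs**
- ρ = 0.5: 0.0818 × √(100/0.1297) = 2.27; Φ(0.31) = **0.622**, matching Table 9.
- ρ = 0: 0.0818 × √(100/0.2455) = 1.65; Φ(−0.31) = **0.379**, matching Table 10.

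**What 100 pairs can detect at 10% exposure**
- Odds ratio 3.0: 0.953 (Table 9) and 0.782 (Table 10).
- 80% power requires an odds ratio of 2.34 (ρ = 0.5) to 3.07 (ρ = 0).
- 86% power requires 2.51 to 3.35.

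**Cell-wall-deficient forms (section 3.6.4).** The cited positivity is about 80% in patients and under 15% in volunteers. At 80% and 15% the odds ratio is (0.80/0.20)/(0.15/0.85) = 22.7. With 100 pairs and ρ = 0, ψ = 0.95 − 0.24 = 0.71, and 0.65 × √(100/0.71) − 1.96 = 5.75, so power is above 99.9%.

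**The case against.** The best defence is that nothing was miscalculated. The 86% is a correct reading of Table 7, and section 1.5.1 sends the reader to the chapter where Tables 8, 9 and 10 are printed. The sentence is an illustration at 180 pairs and makes no claim about 100. Section 12.2.1 expects matching to produce positive correlation, so 60% is the pessimistic end. The paragraph rests on large effects, and for those 100 pairs are often enough.

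Most of this is fair and limits the point to wording. It does not rescue the claim of a minimum. The sentence is specific to an odds ratio of 2.0, a positive correlation need not be as high as 0.5, and the omitted correlation decides whether the figure is 86% or 60%.

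A reader might infer four stronger things, none of which the protocol supports:
- *That no substudy has 180 pairs.* The HLA size is not given and the Kveim size is not readable. Only the stated sizes can be compared.
- *That the substudies are generally underpowered.* The range of 38% to 62% applies to an odds ratio of 2.0 at 10% exposure. The cell-wall-deficient-form study has ample power for its hypothesised effect. Immunogenetics, with 360 pairs, has 0.880 even at correlation 0 (Table 6).
- *That the same formula condemns the differential display and T-cell projects.* One is a discovery screen and the other a study of T-cell clones. Neither is described as testing a binary exposure in matched pairs.
- *That a null PCR result would be taken to exclude an infectious cause.* Section 3.6.3 does not say so, and section 3.7 describes the study as generating hypotheses for further investigation. No caveat there is called for.

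**Conclusion.** The point holds as a misstatement in one overview sentence. For 180 pairs, an odds ratio of 2.0 and 10% exposure, the protocol's tables support 60.1% to 86.2% depending on correlation. The stated minimum overstates the conservative end by 26.1 percentage points (86.2 − 60.1). The size is also poorly chosen: no stated substudy size is 180, and the two infection substudies have 100 pairs, where the corresponding range is 37.9% to 62.2%.

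The conclusion rests on the protocol's own formula and tables and on its description of correlation 0 as conservative. It does not depend on knowing the true correlation. It does not show that any particular substudy is too small: the PCR search states no expected effect, so its power against the effect of interest cannot be determined. The design is unaffected. The sentence should be corrected because it is the overview's power statement for substudies.

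**What to change.** In section 1.5.1, replace the minimum of 86% with a range and its assumption: for 180 pairs, 10% of controls exposed and an odds ratio of 2.0, power is 60% (correlation 0) to 86% (correlation 0.5).

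Add one sentence for the size that the infection substudies actually use: with 100 pairs and 10% of controls exposed, power is 38% to 62% for an odds ratio of 2.0 and 78% to 95% for an odds ratio of 3.0, at correlations 0 and 0.5 respectively. Cite Tables 7 to 10.

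All of these figures are already in Chapter 12, so no new calculation, change of sample size or change of procedure is needed. The only cost is that the overview reads less favourably at an odds ratio of 2.0.
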